### 9.2.2. Secondary Efficacy Endpoint Analysis

Unless otherwise stated, all data up to Week 24 will be summarized, and data for the specified time points up to Week 24 will be analyzed.

The change from Baseline for the daily average and worst pain intensity in the bone metastasis index cancer pain site will be summarized for each week from 1 to 24. The change from Baseline to Weeks 1, 2, 4, 6, 8 (Worst Pain), 12, 16 and 24 will be analyzed using analysis of covariance (ANCOVA) as described above, using multiple imputation.

A secondary analysis for the change from Baseline in the daily average pain scores will use a repeated measures mixed effects model, on the available data over Weeks 1 to 24. Estimates for treatment groups and treatment difference for Weeks 1, 2, 4, 6, 8, 12, 16 and 24 will be shown. Additional secondary analysis for the change from Baseline to Week 8 and 16 in the daily average pain will use single imputation Last Observation Carried Forward (LOCF) and Baseline Observation Carried Forward (BOCF) for missing data.

The mean of the subject's average and worst pain in the non-index cancer sites, over all non-index sites (for up to 2 sites per subject) and for visceral non-index cancer sites will be calculated for Baseline and for each week, and for the change from Baseline. The change from Baseline to Weeks 1, 2, 4, 6, 8, 12, 16 and 24 in average and worst pain in the non-index cancer pain sites will be analyzed using analysis of covariance (ANCOVA) as described above, using multiple imputation. An additional analysis will utilize only those sites where Baseline average/worst pain is at least 5. If a subject has no nominated non-index sites (first analysis) or no nominated non-index sites where Baseline is at least 5 (second analysis) then that subject would be excluded from the respective analysis.

Additional ANCOVA analyses with multiple imputation for the primary endpoint will be used to examine the interaction of treatment group with study site, Baseline pain score, type of primary cancer (eg, breast, lung, etc), Baseline opioid use and the stratification parameters.

The change from Baseline to Weeks 2, 4, 8, 16, and 24 in the CCI [REDACTED] will also be summarized, and analyzed using the ANCOVA main effects model as described above with multiple imputation.

For the daily worst and average pain (in the index site) response efficacy endpoints (defined by a  $\geq 30\%$ ,  $\geq 50\%$ ,  $\geq 70\%$  and  $\geq 90\%$  change from Baseline to Weeks 1, 2, 4, 6, 8, 12, 16 and 24), will be summarized and analyzed using logistic regression for binary data, with model terms for Baseline average/worst pain subscale score, stratification variables, and treatment group. Imputation for missing data will use both LOCF and BOCF, where imputation with BOCF will lead to the subject being assessed as a non-responder for the response endpoint at a particular time point. Also, in order to closely match the primary imputation analysis, a mixed BOCF/LOCF imputation for response endpoints will be used. In this analysis BOCF imputation (ie, a subject would be a non-responder) would be used for missing data due to

### 9.3.4. Opioid Use and Opioid Adverse Effects Analysis

Opioid data from subjects randomized to the tanezumab 10 mg treatment group will only be summarized, and not included in statistical analyses of opioid use data.

Average daily opioid consumption (mg of morphine equivalent dosage) and average number of doses of rescue opioid consumption per week will be summarized for each week up to Week 24. Percent change from Baseline in average daily opioid consumption will be analyzed using ANCOVA on the rank scores with treatment and the stratification variables as factors. The average number of doses of rescue opioid consumption per week will be analyzed using a negative binomial model taking into account Baseline daily average pain and Baseline opioid use.

The number of doses of rescue medication per week will be summarized by treatment group for each week up to Week 24. The total number of doses of rescue medication in Weeks 1, 2, 4, 8, 16, and 24 will be analyzed using a negative-binomial regression model using the log-total number of days of data collection as the subject offset variable. The resulting analysis will show the estimated rate of opioids taken as rescue medication for each week. This estimated rate will be shown by treatment group with standard error and 95% CI. The ratio of the opioid usage rate between tanezumab + opioid versus opioid alone will be shown (with standard error and 95% CI).

The Opioid-Related Symptom Distress Scale (OR-SDS) is a questionnaire on the frequency, severity and level of bother of 10 symptoms. For each symptom the mean of the frequency, severity and bother is calculated to become the Multi-Domain Average (MDA). These are the four dimensions for each symptom. The mean of each dimension over all symptoms is calculated to become the frequency, severity, bother and MDA composite scores. Each of the four dimensions will be summarized by treatment and treatment difference for the 10 symptoms and the overall composite, a total of 44 sets of summary measures. The MDA for each symptom and the four dimensions for the composite score will be analyzed for each time point. The analysis of this data will use a mixed effects repeated measures model and show analysis results for the change from Baseline to Weeks 2, 4, 8, 16, and 24.

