#### **2.2.2.2. Opioid Use and Opioid Adverse Effects Measures**

- Average daily total opioid consumption (in mg of morphine equivalent doses) at Weeks 1, 2, 4, 6, 8, 12, 16 and 24.
- Average number of doses of rescue medication required per week at Weeks 1, 2, 4, 6, 8, 12, 16 and 24.
- Change from Baseline in the weekly Opioid-Related Symptom Distress Scale at Weeks 2, 4, 8, 16, and 24.

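### The only week list for the rescue-dose model in Section 9.3.4 omits endpoint Weeks 6 and 12, and the section does not say that its two paragraphs describe one model

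*Protocol*

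**What the plan says.** The endpoint is defined in Section 2.2.2.2, and identically in the Protocol Summary: "Average number of doses of rescue medication required per week at Weeks 1, 2, 4, 6, 8, 12, 16 and 24".

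Section 9.3.4 then deals with it twice.

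- **Average-dose paragraph.** "The average number of doses of rescue opioid consumption per week will be analyzed using a negative binomial model taking into account" two covariates, one for pain and one for opioid use, both at Baseline. It names no offset and no weeks for the model.
- **Total-dose paragraph.** "The total number of doses of rescue medication in Weeks 1, 2, 4, 8, 16, and 24 will be analyzed" with a "negative-binomial regression model using the log-total number of days of data collection as the subject offset variable". It names no covariates. It is the paragraph that specifies the output: an estimated rate by group and a rate ratio, each with standard error and 95% CI.

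Both paragraphs also promise a weekly descriptive summary; the second reads "The number of doses of rescue medication per week will be summarized by treatment group for each week up to Week 24".

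Section 9.2.2, on secondary efficacy endpoints, has a general sentence that, unless otherwise stated, "data for the specified time points up to Week 24 will be analyzed".

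On total opioid consumption, Section 9.3.4 says: "Percent change from Baseline in average daily opioid consumption will be analyzed using ANCOVA on the rank scores with treatment and the stratification variables". Baseline dose is not among the terms.

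**The concern.** An endpoint set at eight time points should have an analysis that covers eight, or a stated reason why it does not. Here the only weeks attached to the rescue-dose model number six, and no reason is given. An analyst following Section 9.3.4 literally would report no rate ratio for Weeks 6 and 12; one following Section 2.2.2.2 would report it.

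The split description adds a second uncertainty. The text does not say that the covariates in one paragraph and the offset in the other belong to the same model, so it is not stated whether the reported rate ratio is adjusted for Baseline pain and Baseline opioid use. What is at stake is the completeness and the precision of one secondary result.

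**Working it through.** **1. Week lists side by side.**

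| Measure | Endpoint weeks (Sections 2.2.2.1, 2.2.2.2) | Analysis weeks (Sections 9.2.2, 9.3.4) | Missing |
|---|---|---|---|
| Rescue doses | 1, 2, 4, 6, 8, 12, 16, 24 | 1, 2, 4, 8, 16, 24 | 6, 12 |
| OR-SDS | 2, 4, 8, 16, 24 | 2, 4, 8, 16, 24 | none |
| Index-site pain responders | 1, 2, 4, 6, 8, 12, 16, 24 | 1, 2, 4, 6, 8, 12, 16, 24 | none |

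For OR-SDS, Section 9.3.4 will "show analysis results for the change from Baseline to Weeks 2, 4, 8, 16, and 24", exactly as its endpoint is set. For rescue doses, 8 − 6 = 2 time points are lost, and no extra ones appear.

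**2. Is there a data reason?** No. Under Section 7.1.2 opioid use, including rescue doses, is recorded daily to the Week 8 visit and then weekly by 24-hour recall to Week 24. Week 6 therefore has daily data, and Week 12 has the same kind of record as Weeks 16 and 24. The clinic schedule does not explain the list either: Section 6.2 has no visit at Week 1, yet Week 1 is on it.

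**3. One model or two?** For a count Y recorded over d days, the usual model for a rate is log E(Y) = log(d) + treatment + covariates. The total-dose paragraph supplies Y and log(d); the average-dose paragraph supplies covariates. The two fit together, and only one set of outputs is specified. The text does not say that they are to be joined.

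**4. What if the Baseline terms were left out?** The protocol gives no rescue-dose rate or variance. Its only power figure is for the primary endpoint: n = 2 × (1.960 + 1.036)² × 2.0² / 1.0² = 71.8, so 72 per group, which reproduces Section 9.1. That supplies the arm size and nothing more. Everything else below is assumed: about 1 rescue dose per day, and either no effect or a 30% reduction (log rate ratio ln 0.7 = −0.357).

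- *Complete diaries, 3000 trials per setting.* Baseline covariates explain 10%, 25% or 40% of the between-subject log-variance. The mean log rate ratio at Week 8 is −0.35 to −0.36 with or without them. The variance without covariates, relative to a model with offset, Baseline terms and strata, is 1.09–1.11, 1.32–1.36 and 1.56–1.67 at Week 8, and 1.03–1.17 at Week 16 (one recall day).
- *Unequal missing diary days, 600 runs per scenario.* Bias in the log rate ratio is at most 0.02. The empirical standard error without covariates is 1.075 to 1.331 times that with them. With a single recall day the ratio is 1.015 to 1.125.

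These figures show direction only. In the first set the comparison model also contains the strata, so the ratio is not purely the effect of the Baseline terms. The model without covariates rejects a true null in 6.8%, 7.5% and 7.9% of the Week 8 runs, against a Monte Carlo error of √(0.05 × 0.95 / 3000) = 0.4 points. Its nominal tests are therefore somewhat liberal, and its power is not a clean comparator. None of this measures the missing weeks.

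**5. The opioid rank ANCOVA (a separate suggestion).** With an assumed log-SD of 0.9, the variance ratio without versus with ranked Baseline dose is 1.29, 1.15, 1.04 and 1.01 at log-correlations of 0.5, 0.7, 0.9 and 0.97. The reduction, 1 − 1/ratio, is about 22%, 13%, 4% and 1%. Type I error is 4.5–5.5% either way. Through Week 8, Section 6.2.2.1 limits the dose to 10% above Baseline. If doses then ran uniformly on the log scale from 50% to 110% of Baseline (assumed), the correlation would be 0.9 / √(0.81 + (ln 2.2)²/12) = 0.97, where the gain is negligible.

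**The case against.** The strongest reply is that the two paragraphs are one analysis set out in two steps, that only one set of outputs is requested, and that joining covariates to an offset is ordinary SAP work, which Section 9 leaves to the SAP. That stands. A reader might infer two competing models and hence a contradiction, but the text supports no more than an ambiguity.

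A reader might also take simulated disagreement as the size of the problem: the two paragraphs, fitted separately, differ on significance in 10% to 22% of simulated trials at Week 8. The documents do not support that use. With every diary complete the offset is a constant, so the disagreement comes only from treating the second paragraph's silence on covariates as their absence. An unnamed covariate is SAP detail, and the rates are assumed.

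Thirdly, the general sentence in Section 9.2.2 might be thought to restore Weeks 6 and 12. It could do so for the average-dose paragraph, which names no weeks. But it sits in the efficacy section, while rescue doses are listed separately under Section 2.2.2.2, and it yields where something else is stated. The total-dose paragraph states six weeks. The mismatch survives, although both weeks keep their descriptive summary and no data are discarded.

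**Conclusion.** The week mismatch is a true inconsistency in the protocol: 2 of 8 endpoint time points have no clearly planned model-based comparison. The split model description is a lesser matter of clarity. Together they are a minor point on one secondary endpoint; the primary analysis, alpha and sample size are unaffected.

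Neither paragraph gives a materially biased rate ratio under the assumptions tried. Omitting the Baseline terms would cost precision, but the loss depends on rates, dispersion and covariate strength that the protocol does not give. The week mismatch itself needs no assumption; it follows from comparing the two lists.

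**What to change.** In Section 9.3.4, and in the SAP to match, state one rescue-dose model: negative binomial on total doses recorded in the week; offset log(days recorded); terms for treatment, Baseline daily average pain, Baseline opioid use and the two stratification factors; at Weeks 1, 2, 4, 6, 8, 12, 16 and 24. The stratification factors are a free improvement, since neither paragraph names them. Keep average doses per week as a descriptive summary and delete the duplicate sentences.

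A separate free improvement, not the correction of an error: add ranked Baseline opioid dose to the rank ANCOVA of percent change in opioid consumption. The gain is likely to be small through Week 8.

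The cost is wording. Every variable is already collected, and no visit, sample size or primary analysis changes.

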### **4.3. Randomization Criteria**

The following criteria must be met to be eligible for randomization:

1. There have been  $\leq 3$  IR rescue episodes per day for breakthrough pain from Day -3 to Day -1 during the Baseline Assessment Period.
2. The mean value of the average daily pain scores for the index bone metastasis cancer pain site from Day -5 to Day -1 during the Baseline Assessment Period must be  $\geq 5$ ; Subjects must complete interactive response technology (IRT) pain assessments on at least 3 of the 5 days during the Baseline Assessment Period.
3. There are no intolerable opioid side effects in the judgment of the subject from Day -3 to Day -1 during the Baseline Assessment Period.
4. The Patient's Global Assessment of Cancer Pain must be "fair", "poor" or "very poor" at the Baseline Visit.
5. Radiologic eligibility must have been confirmed by the Central Reader during the Screening Period, Baseline Assessment Period or at the Baseline Visit.

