### **6.1.2. Baseline Assessment Period (BAP, Days -5 to -1)**

The purpose of the Baseline Assessment Period is to determine the Baseline pain value for each subject and to document that the subject’s background opioid regimen is sufficiently robust to minimize the need for opioid IR rescue but also tolerable as judged by the subject. These data will confirm that Randomization Criteria 1, 2 and 3 have been met. Refer to [Section 4.3](#) for Randomization Criteria details.

Subjects who remain eligible and who are tolerating a stable ATC regimen of opioids can begin the Baseline Assessment Period approximately 5 days prior to the Baseline (Day 1) randomization visit.

During the Baseline Assessment Period, the subject will record daily pain scores for his/her cancer pain sites and opioid medication use via the IRT (refer to [Section 7.1.1](#)). The daily average pain score in the index bone metastasis site and daily opioid use collected via IRT should be reviewed by study site staff to assess compliance with the subject diary and need for dose adjustments. Each day the subject will record via IRT (subject diary) the amount of ATC and IR opioid taken, the number of times rescue medication was taken, and whether or not opioid pain medication side effects are tolerable.

**Note:** In the event a subject misses an assessment day in this Baseline Assessment Period, the schedule may be adjusted to acquire the 5 days of assessment entry into the IRT. Study sites will monitor the IRT reports for compliance with diary recordings and rescue medication use and reschedule those subjects who fail to provide at least the final 3 days of diary data (Day -3 to Day -1).

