## **6.2.2. Double Blind Treatment Period**

### **6.2.2.1. Background Opioid Use**

After randomization and through Week 8, all subjects will continue to take the opioid regimen or morphine equivalent dose used during the Baseline Assessment Period. The average of the total daily opioid doses (ATC + IR) taken during the Baseline Assessment Period will be used as the Baseline total daily opioid dose.

Beginning on Day 1 and through Week 8, the average total daily dose of opioids between study clinic visits should not exceed the Baseline total daily morphine equivalent opioid dose by more than 10%. Subjects who require an opioid dose more than 10% greater than the Baseline total daily opioid dose should discontinue the Double-Blind Treatment Period for insufficient clinical response or disease progression ( per investigator's judgment) and enter the 6-month Safety Follow-Up period (refer to [Section 6.4](#)). Opioid dose reduction will be allowed if the subject experiences intolerable opioid side effects, if pain decreases or if the subject requests dose reduction. Once reduced, the opioid dose may be re-increased if needed for pain relief, but should not exceed the Baseline total daily morphine equivalent opioid dose by more than 10%.

Following the Week 8 clinic visit, subjects will remain on the opioid regimen used during the Baseline Assessment Period but will be allowed to change formulation, increase or decrease the amount of their background opioid medication without restriction if the investigator

considers such changes are necessary. Opioid reductions and increases will be done using accepted clinical guidelines (refer to [Section 6.1.1.2.4](#)).

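### The negative binomial model for weekly rescue doses names Baseline pain and Baseline opioid use but omits the Baseline rescue rate and the randomisation strata, at some cost in precision for a secondary endpoint

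*Protocol*

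**What the plan says.** Section 2.2.2.2 lists the endpoint as "Average number of doses of rescue medication required per week at Weeks 1, 2, 4, 6, 8, 12, 16 and 24". This is a post-Baseline level, not a change from Baseline.

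Section 9.3.4 describes two negative binomial analyses of rescue doses:

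- The weekly average "will be analyzed using a negative binomial model taking into account Baseline daily average pain and Baseline opioid use".
- The total number of doses in listed weeks "will be analyzed using a negative-binomial regression model using the log-total number of days of data collection as the subject offset variable". No covariate is named here. Treatment is implied, because a ratio of rates between groups is to be shown.

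On Baseline data, Section 6.1.2 has the subject enter each day "the amount of ATC and IR opioid taken, the number of times rescue medication was taken", and Section 6.1.1.2.4 asks for the same entries through the Pre-Treatment Period. Randomization criterion 1 in Section 4.3 allows at most three "IR rescue episodes per day for breakthrough pain from Day -3 to Day -1 during the Baseline Assessment Period". Section 6.2.2.1 defines the Baseline opioid dose: "The average of the total daily opioid doses (ATC + IR) taken during the Baseline Assessment Period will be used as the Baseline total daily opioid" … This is an amount of opioid, not a count of rescue doses.

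The stratification variables (ECOG class and concomitant anticancer treatment, Section 5.1) are model terms in the primary ANCOVA (Section 9.2.1), the responder logistic regression (Section 9.2.2) and the rank ANCOVA of opioid consumption (Section 9.3.4).

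**The concern.** When the outcome is a level, each subject's rescue habit before the first injection carries over into it. The protocol deals with this elsewhere. The primary ANCOVA and the responder models contain the Baseline value of their own outcome, opioid consumption is analysed as percent change from Baseline, and the symptom distress scale as change from Baseline. The covariate list for weekly rescue doses does neither and gives no reason.

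There is a design reason to expect Baseline rescue to be informative. Through Week 8 the average total daily dose should stay within 10% above a Baseline that itself includes rescue (Section 6.2.2.1), on a fixed around-the-clock regimen (Section 5.8.2.1). The room for rescue in those weeks is therefore tied to Baseline rescue.

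At stake are the precision of the rate ratio and the risk that a chance difference present before dosing looks like an opioid-sparing effect, or hides one.

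**Working it through.** **The plan's own figure.** The protocol gives no mean, dispersion or correlation for rescue doses and no figure for this endpoint. Its sample size is for the primary endpoint: n = 2(1.960 + 1.036)² × 2.0² / 1.0² = 71.8, so 72 per arm, which reproduces. Everything below uses 72 per arm; all other inputs are assumptions.

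**Size of chance imbalance.** Assume a between-subject SD of 0.9 rescue doses/day. One standard error of the difference between arms is 0.9 × √(2/72) = 0.15/day. The 95% range is ±1.96 × 0.15 = ±0.29/day, or about ±2 doses/week.

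**Setting A.** Lognormal subject rates, mean 1.2/day, CV 0.8, capped at 3/day; 5-day Baseline count; 7-day outcome; no treatment effect; 300 trials per row. The model is fitted with and without log((Baseline count + 0.5)/5).

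| Baseline–outcome correlation | SE without | SE with | Variance reduction |
|---|---|---|---|
| 0.59 | 0.129 | 0.103 | 37% |
| 0.50 | 0.183 | 0.150 | 33% |
| 0.41 | 0.240 | 0.219 | 17% |
| 0.34 | 0.319 | 0.300 | 12% |

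The reduction is 1 − (SE with / SE without)²; the rounded SEs in the first row give 36%. A repeat of this set-up gave 18% to 40%, broadly the same. With a single day of outcome data it fell to about 5–23%, and to 6–14% at a mean of 0.5/day.

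**Setting B.** Gamma subject rates, mean 1/day, dispersion 0.8; Baseline limited to 3/day on Days −3 to −1; 7-day outcome; no treatment effect; 800 trials per row. The shift is the change in the rate ratio for a one-standard-error Baseline imbalance.

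| Latent correlation | Shift, offset only | Shift, + Baseline opioid mg | Shift, + Baseline rescue rate | Variance reduction |
|---|---|---|---|---|
| 0.3 | 3.1% | 3.1% | 0.4% | 1% |
| 0.6 | 6.7% | 6.6% | 0.4% | 8% |
| 0.8 | 8.9% | 8.7% | 0.1% | 19% |

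Baseline opioid mg correlated with the rescue count at only 0.13 to 0.14 in these assumed data, so it removed almost none of the shift.

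**Bias and type I error.** In Setting B the offset-only mean log rate ratio was between −0.008 and 0.003, and the type I error was 5.1% to 5.5%. With the Baseline rescue rate added it was 5.0%, 6.2% and 7.2% (simulation error √(0.05 × 0.95/800) = 0.8 points), so the model-based SE ran slightly short at the highest correlation.

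A third set of inputs (lognormal rates, log-SD 0.9, 600 trials per row) gave variance reductions of 7%, 15% and 25%. Type I error there was above 5% both without (7.0–11.7%) and with (6.5–10.7%) the Baseline rate. It is high either way, so it reflects the fit of the negative binomial form to those data, not the missing covariate.

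**The case against.** The strongest reply is that this is detail for the SAP. Section 9 leaves detailed methodology to that document and lets it modify the plan, and neither sentence in 9.3.4 is a complete model statement, since treatment itself is not listed. This holds for the second description: a reader might infer that it excludes covariates, but it is only silent. It does not hold for the first, where the protocol names its covariates and the list is too short.

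Other points stand:

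- A reader might infer that the planned estimate is biased or the test invalid. Randomisation keeps the estimate unbiased, and its standard error already allows for chance imbalance.
- Setting A's best row can be read as 114 subjects per arm instead of 72 (72/0.63). That is the most favourable assumed case, and its comparison did not include the Baseline pain and opioid terms that the protocol names.
- That Baseline rescue is the strongest predictor, or that subjects differ widely at entry, is plausible but not shown. Section 6.1.2 aims for a regimen that keeps rescue low.
- After Week 8 opioid use is collected weekly by 24-hour recall (Sections 6.2.2.3 and 7.1.2), the regimen may be changed freely (Section 6.2.2.1) and standard-of-care analgesia is allowed (Section 5.8.2.5). Gains at Weeks 12, 16 and 24 should be smaller.
- Section 9.3.4 does not define Baseline opioid use; equating it with the dose in Section 6.2.2.1 is an inference, and that dose includes the rescue amount.
- The diary item is "the number of times rescue medication was taken" while the endpoint counts doses; the protocol does not say that these are identical.

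**Conclusion.** The point holds as an efficiency improvement to a secondary analysis. The stated covariate list omits the Baseline value of the outcome, which is collected daily, and the strata, which neighbouring analyses include. The primary analysis is unaffected.

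The size rests on inputs that the protocol does not supply. Variance reductions run from roughly 1% to 37%, rising with the correlation between Baseline and later rescue use, and are likely toward the lower end after Week 8. These gains come from the Baseline rescue rate alone; the effect of adding the strata was not simulated, and the case for them is consistency with the randomisation and the other models.

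The documents do not support a claim of systematic bias or of type I error inflated by the omission.

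**What to change.** Before unblinding, state one covariate set for the negative binomial model in Section 9.3.4: treatment, Baseline daily average pain, Baseline opioid use, the Baseline daily rescue rate from the Baseline Assessment Period, and the two stratification variables, with the log-days offset. The Baseline rate could enter as log((count + 0.5)/days), with the constant fixed in advance. Define Baseline opioid use, and say whether a diary rescue episode counts as one dose.

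The cost is a sentence or two, no new data, about three model degrees of freedom (one for the rate, one for each binary stratum) and a prespecified rule for zero counts. Because the model-based SE ran slightly short in the most correlated case of Setting B, the form of the Baseline term deserves a check when it is prespecified.
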